15.0 Risks to Subjects*

Protection against risk will begin with careful clinical management and education of patients and families. Informed consent will be obtained at the enrollment phone visit and include specific details of all risks, including consequences of psychiatric illnesses.

Baseline & Follow Up Assessments conducted by Pittsburgh/ETUDES Center

The risks due to phone interview assessments and self-reported questionnaires are: 1) discussion of potentially upsetting information, 2) loss of confidentiality, and 3) assessment burden. The interviewers will all be trained and skilled interviewers who can assess and monitor the reaction to questioning about sensitive topics; interviewees will be given the option of not responding or ending the interview. The assessment has been streamlined to limit assessment burden by using only a few measures per outcome domain. Each phone assessment should take about 30-60 minutes. Participants will be appropriately compensated for their time. Another potential risk is the disclosure of abuse. We are very familiar with assessment, management, and reporting of child maltreatment as this is considered part of standard clinical care in psychiatry and pediatric primary care. These incidents are common during trials, and we have standard for both managing and reporting these incidents. In all cases, state law is followed. Risk management procedures involved referral if symptoms do not improve or worsen and procedures to protect confidentiality are in place, as well as annual review of study progress by a Data Safety Monitoring Board. Risk management procedures are in place to involve communication between study staff and primary care physicians if there are indicators of clinical deterioration (e.g. suicidal thoughts emerge in youth interview and youth cannot contract for safety), to protect confidentiality. Every effort will be made to schedule assessments at times that are suitable for participants and families (after school or work) as needed in order to minimize negative impact on other important work, school, or social activities.

PROTOCOL TITLE: The Center for Enhancing Treatment & Utilization for Depression and Emergent Suicidality Phase 1b-Study 3-BRITEPath

Audio recording

Measures will be taken to upload recordings to a secure network drive monitored by the University of Pittsburgh IT department and erased from the recording device.

BRITE Intervention:

Risk management procedures involve referral if symptoms worsen or patients do not make significant gains and procedures to protect confidentiality are in place. Parents will be advised to monitor their youth's phone/device to avoid their access of explicit or unwanted material, as they typically would with any device intended for their child's personal use. Additionally, study PI & CO-I will be available to consult with clinical staff about the intervention in cases where the intervention may not be providing any gain to the patient or if symptoms worsen. If a mental health staff identifies that their patient is at imminent risk for suicidal behavior, they will follow their usual standard of care in managing these symptoms. The BRITEPath intervention will in no way interfere with the usual standard of care practices of managing imminent risk in pediatric primary care.

The app is meant to measure distress, not suicidality, so there is no time in which it will trigger response from providers in real-time or outside of work hours. The app will direct patients to deploy their safety plan if they are in crisis, which includes numbers for 24-hour crisis hotlines. The contents of the participant's safety plan will be available, even when the participant does not have access to wifi/data. Some portions of the app, e.g. portions that link to websites or youtube videos, will not be available without internet connection. Warnings are programmed within the app to notify participants when a poor connection is in place that may limit their access to certain parts of the app.

Minimizing Risk of Suicidal Behavior

Since participants may be eligible who exhibit current suicidal ideation, the biggest risk for these participants is their risk for suicidal ideation, behavior, or even suicide. In relation to assessment, there is now clear evidence that asking about suicidal ideation and behavior will not increase the risk for such behavior. Further, through repeated assessments of psychopathology, suicidal ideation, and behavior, we provide an additional safety net for the participants and their families beyond that which would occur in clinical care. As noted above, the research team will be appropriately trained in clinical management of adolescent suicidal ideation and behavior. Both the Pittsburgh research team and local site will manage suicidal risk using suicide prevention procedures established by the American Academy of Child and Adolescent Psychiatry (AACAP) Practice Parameters on Suicidal Behavior. These include risk assessment, identification/modification of precipitants, and safety planning. Suicide risk will be managed within the primary care setting for youth in both the TAU and intervention group.

PROTOCOL TITLE: The Center for Enhancing Treatment & Utilization for Depression and Emergent Suicidality Phase 1b-Study 3-BRITEPath

The ETUDES Center will generate “protocol alerts” for the Pittsburgh/ETUDES clinical assessors to assist with the detection and management of suicidality among adolescents. If suicidal ideation or behavior is endorsed at follow-up phone visits, trained clinical interviewers will engage in assessment of the adolescent's risk of attempt. A safety plan will be developed with youth expressing any suicidal ideation, if he or she does not already have one. The parent will be notified and the clinical interviewer will make a decision as to whether the patient is at imminent risk or not. Assuming that the patient can commit to a safety plan and the parent is agreeable, we already have obtained consent to notify the pediatrician and we will obtain permission to contact their therapist if they are in treatment. If the patient cannot commit to a safety plan and/or the clinical interviewer is concerned that the patient is at high imminent risk, this will be discussed with the parent, and the clinician will set up a conference call with a crisis hot line to further evaluate the patient. If the patient refuses or hangs up, then the crisis team will be contacted who will help determine further action. Outside of Allegheny County/Pittsburgh, PA, the crisis line is the National Suicide Prevention Lifeline, which can provide on-phone support, and can access emergency visits to the home based on local resources. If the assessor is uncertain about assessment of suicidal risk, he or she will contact one of the Center on-call clinicians to either consult or speak directly with the patient and family. Similar procedures have been operative in studies of [name] including the Familial Pathways study (R01 MH056612), which assessed youth with parental loading of depression and suicide attempt and the EDSTARS study (U01 MH104311), which assessed adolescent's suicide risk within pediatric EDs. If the interviewer is uncertain about how to proceed, the PI, [name] or Co-I, [name], will be available as a back up.

All aspects of the research interaction with participants will be private. Research staff will complete the phone assessments in a private, confidential location. In addition, research staff will ask the parent and youth prior to the start of the phone assessment if they are in a private location where they feel comfortable reporting sensitive information to the interviewer. Additionally all identifiable information will be held either in a locked filing cabinet or in a secure online database with security and confidentiality measures implemented and maintained by the University of Pittsburgh IT department.

In the event that additional risks are found out, participants will be notified immediately of any risk it may pose to them. A copy of the verbal consent script will be provided to participants in the form they request (i.e. mailed, emailed).

16.0 Potential Benefits to Subjects*

This research project provides an immediate app-guided intervention to reduce suicidal distress.

Participants may also derive a sense of accomplishment from participation in research and contributing to the knowledge of screening, triage, and management of adolescent/young adult depression and suicidal ideation and behavior.

17.0 Data Management* and Confidentiality

A stepped wedge design was selected for both ethical considerations and feasibility. A stepped- wedge cluster randomized trial design involves the sequential random rollout of an intervention over multiple time periods following a “baseline” period when no cluster has been exposed. The crossover is typically in one direction, from control to intervention, and continues until all of the clusters receive the intervention with observations taken from every cluster and at each time period. All 3 studies in the ETUDES Center, and specifically, BRITEPath, will utilize this design. Prior to study start, each site will be randomly assigned to switch from.

Treatment As Usual (TAU) to the intervention. In the proposed stepped wedge design, all practices start with TAU (i.e., PCP referral to embedded MH care) and are randomized to transition to implement BRITEPath at different times. All clinics will be initially monitored for at least 2 months during TAU, followed by a staggered adoption of BRITEPath. During each time period, a new clinic will begin to use BRITEPath (order determined by block randomization). A webbased system will randomly assign the next clinic to begin.

With regard to the stated hypothesis: We will perform multilevel modeling to explore time- and intervention-level factors associated with BRITEPath’s use. We will first conduct t-tests for continuous variables and chi-square tests for categorical variables to examine baseline differences in demographic and clinical variables. We will use generalized linear mixed models (nesting for site) to examine between intervention differences in readiness. Distinguishing characteristics will be included as covariates in models examining treatment effects.

Due to the pilot nature of this study, sample size and power considerations center around the precision of confidence interval (CI) width estimation for feasibility outcomes. In this development phase (Aim 1), a sample size of 50 affords us a 95% CI width of no more than 0.28.

We will evaluate uptake of BRITEPath by community pediatric clinics utilizing the RE-AIM framework and determine implementation outcomes as follows: Reach: Compare demographic and clinical characteristics of those patients who do versus do not (opt-out) get BRITEPath in practice for sample representativeness. Efficacy: Measure the percentage of patients for whom clinically significant reductions in depressive symptoms and suicidality as well marked improvements in functioning are obtained. Adoption: The percentage and characteristics of MH clinicians who participate in the BRITEPath study. Implementation: The percentage and characteristics of MH clinicians who follow through with BRITEPath use procedures (examining different components of app use). Maintenance: Extent BRITEPath is utilized and predictors of utilization after research support has been withdrawn.

Identifiers that will be collected via electronic data management include: name, email address, phone numbers, medical record numbers, and social security numbers for payment only. We will be collecting location data (addresses), date information (Date of Birth, admission dates, etc), and sensitive data (such as protected health information, etc).

The data will be collected on a web-based database. Data will not be stored with participant identifiers and will be coded with a participant ID #. Data may be stored on UPMC owned or University owned computers in research offices. Documents containing data will be deidentified and encrypted with a password to which only the research staff have access. The following storage devices will be used:

- Google cloud storage will be used for deidentified summary data collected from NuRelm’s webportal only. NuRelm is the app developer of BRITEPath suite of tools.

PROTOCOL TITLE: The Center for Enhancing Treatment & Utilization for Depression and Emergent Suicidality Phase 1b-Study 3-BRITEPath

- University or UPMC owned laptops and desktops
- Amazon Web services stores deidentified data of one of the measures University of Pittsburgh collects through the cat-mh.com adaptive measures. Only deidentified data will be stored here.
- UPMC MyCloud/One Drive will be used to release only identifiable data and deidentified data that is necessary for ceded/partner sites to complete data analysis per Data Use Agreements with the University of Pittsburgh
- Pitt Box will be used to share data between investigators and will only contain deidentified data.
- University of Pittsburgh CSSD Network Operations Center Managed Server: Participant questionnaire data and interview data collected during baseline and follow up phone visits will be stored on the web database created by the Center for Clinical Trials Data Collection (CCDC) on the University of Pittsburgh managed server. NuRelm will create the portal and application tables that store intervention data and communicate to the CCDC web database will be stored on this server. Only authorized users to the tables and portals/websites developed and stored on this server have access with specific login and password information given to them by study administrators/PIs. Only particular views to the data are given to particular individuals on the study. Individuals are only given access to what they absolutely need to complete their role on the study.

Any hard copy or paper data will be stored by ID # in a locked cabinet in a locked office to which research staff only have access. No research data will be stored with identifiers on it. The key/link between the ID# and participant identifiable information will be kept separately in locked cabinets in locked research offices or in encrypted electronic documents on a Pitt or UPMC owned computer behind the firewall.

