PROTOCOL TITLE: The Center for Enhancing Treatment & Utilization for Depression and Emergent Suicidality Phase 1b-Study 3-BRITEPath

parents and patients. The simplicity and flexibility of BRITEPath would allow for its dissemination to reach beyond specialty MH clinics and is consistent with the NIMH 2015 Strategic Plan emphasizing the need for individualized strategies to improve patient outcomes.

It is impractical for MH clinicians to offer BRITEPath only sometimes and to some patients and not others. Although a cluster randomized trial could address this issue, this design is not feasible for a pilot study. Thus, we will utilize a stepped wedge design in which all practices start with Treatment As Usual (TAU) initially and are randomly chosen to transition to BRITEPath at different times. All clinics will be initially monitored for at least two months during TAU for the main outcomes of fidelity to delivery of the intervention. This will be followed by a staggered adoption of BRITEPath. At each time period, a new clinic will begin implementing the intervention. Block randomization determines the order each clinic begins BRITEPath. Each time period (approximately 3 months), a web-based system will be used to assign the next clinic to begin using BRITEPath.

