13.0 Recruitment Methods

Participants will be screened through site staff and clinicians under the direction of the site investigators. Clinicians taking part in the research project will scan intakes via telehealth (or in person when the COVID-19 pandemic allows for in person procedures) appointments for eligibility by reviewing electronic medical record information and chief complaint for presenting to appointment. At time of appointment, trained clinician/research site staff will discuss BRITEPath study option and complete eligibility screening questions.

Flyers and informed consent fact sheets used to discuss procedures and risks/benefits may be emailed or mailed for the patient to view at any time.

Participants are provided with the BRITE app during this appointment following completion of the intervention. Upon responding to follow up phone calls made by Pittsburgh/ETUDES Center research staff, the participants will be paid up to \$180 on a visa gift card type card and mailed to participants' address.

Baseline visit phone call after intervention completed at site: \$40

Week 4 Follow Up call: \$60

Week 12 Follow Up call: \$80

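### Covariates for the effect models are chosen by baseline significance tests, a screen that at N = 50 loses precision and may adjust for early effects of BRITEPath

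*Combined protocol and SAP*

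**What the plan says.** The analysis text is in section 17.0. It begins with "t-tests for continuous variables and chi-square tests for categorical variables to examine baseline differences in demographic and clinical variables". The next sentence is about readiness: "We will use generalized linear mixed models (nesting for site) to examine between intervention differences in readiness". Then comes the covariate rule: "Distinguishing characteristics will be included as covariates in models examining treatment effects".

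The section gives no significance level, no list of candidate variables and no name for the groups compared. TAU v BRITEPath is the natural reading, as is the link between the tests and the covariate rule. Site nesting is stated only for the readiness model. Time appears only in an exploratory model: "We will perform multilevel modeling to explore time- and intervention-level factors associated with BRITEPath’s use".

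The design is a stepped wedge by clinic. Section 6.0 says "At each time period, a new clinic will begin implementing the intervention", with periods of about three months. Section 13.0 lists the first paid assessment as "Baseline visit phone call after intervention completed at site", and section 22.0 gives the same order: consent, intervention, then research calls. Section 6.0 lists what the calls collect, including suicidality scales, readiness for treatment and attitudes toward seeking help.

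**The concern.** A significance test of baseline difference is a poor guide to what belongs in an effect model. What matters for precision is how strongly a variable predicts outcome, and the test does not measure that. What matters for bias is the size of a real imbalance in a prognostic variable, and a test with 50 participants will often miss it. Real imbalance is plausible here, because section 6.0 concedes that assignment cannot be concealed once a clinic crosses over.

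The timing of the baseline call adds a second problem. If BRITEPath has already changed a clinical measure by the time of the call, that measure will tend to differ between conditions. The rule then brings it into the model as if it were a baseline characteristic, which removes part of the effect being estimated.

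Section 6.0 says the pilot's effect sizes would be used to design a larger trial, so both the precision and the centring of the estimate matter beyond this study.

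**Working it through.** **The plan's own figure.** "a sample size of 50 affords us a 95% CI width of no more than 0.28". The Wald width at p = 0.5 is 2 × 1.96 × √(0.25/50) = 0.277, so the figure reproduces. It concerns feasibility proportions and gives no support to the covariate rule.

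**Inputs.** N = 50 and about 10 per site (sections 12.0 and 26.1), so about 50/10 = 5 clinics. Assumed, because the documents do not state them: a two-sided 5% level, 10 to 20 candidate variables, a 25 v 25 split for the power figures, an ICC of 0.05 to 0.10, six periods, and a correlation of 0.6 between covariate and outcome.

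**1. Missed imbalance.** With 25 v 25, the smallest observed difference reaching p < 0.05 is t(0.975, 48) × √(2/25) = 0.57 SD. From the non-central t with non-centrality d/√(2/25):
- true d = 0.3: flagged 18%, missed 82%
- true d = 0.5: flagged 41%, missed 59%

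**2. Chance covariates.** For k independent tests with no true difference, P(at least one) = 1 − 0.95^k. This is 40% for k = 10 and 64% for k = 20. Correlated variables lower it: at pairwise correlations of 0.3 to 0.5, 15 tests give about 45% to 37%, against 54% if independent.

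**3. Precision.** The simulation used 5 clinics, 6 periods and 10 participants per clinic (27 TAU, 23 BRITEPath), with ICC 0.05. There was one prognostic covariate among 10 candidates, and clinic and period were in the model.

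| Covariate rule | SD of effect estimate | Type I error |
|---|---|---|
| none | 0.498 | 5.4% |
| significance screen | 0.497 | 5.5% |
| prognostic covariate pre-specified | 0.407 | 5.1% |

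The screen picked the prognostic covariate in 6% of trials. Pre-specifying it reduces the SD by 1 − 0.407/0.497 = 18%, close to the theoretical 1 − √(1 − 0.6²) = 20% before losses from the extra parameter. The variance ratio is (0.497/0.407)² = 1.49, so using the screen is roughly like discarding a third of the participants (1 − 1/1.49 = 0.33). A second simulation under the same stated assumptions gave SDs of 0.56 with the screen and 0.46 with pre-specification, again an 18% reduction.

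**4. Adjusting for an early effect.** Let the true total effect be 0.50 SD, and let a call variable correlated 0.6 with outcome already carry an early effect e in the same direction. Always adjusting for it would give about 0.50 − 0.6e, which is 0.32 at e = 0.3 and 0.20 at e = 0.5. The screen adjusts only when the variable is flagged. In simulation the mean estimate is then about 0.42 at e = 0.3 and 0.32 at e = 0.5; without the adjustment it stays near 0.50. The loss exceeds flag rate times full adjustment (0.18 × 0.18 = 0.03 at e = 0.3, against an observed 0.08). The unflagged trials tend to be those in which chance imbalance ran against BRITEPath, and they stay uncorrected.

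**5. Ignoring clinic in the tests.** With no true difference, the participant-level t-test flags about 6% to 7% at ICC 0.05 to 0.10, against a nominal 5%. Most clinics contribute participants to both conditions, so the inflation is small.

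**The case against.** Section 17.0 never states a p-value rule. The sentence about distinguishing characteristics follows the readiness model rather than the tests, so the link is an inference. Nor does the text say that nothing else will be adjusted for; baseline severity might enter as a repeated measure. These points stand as limits on the reading. They do not rescue the rule, because on any reading covariates enter according to observed differences and none is named in advance.

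A reader might infer that testing without regard to clinic and period gives seriously wrong error rates. The check does not bear this out: ignoring clinic adds one or two percentage points at modest ICC. A calendar drift in case mix does raise the flag rate (a 0.5 SD drift to about 13%), but it also creates a real expected difference of about 0.23 SD between conditions. Those flags are detections, mostly missed, and should not be counted as false positives.

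A reader might also infer that the treatment test is invalid. Its type I error stayed near 5% under all three covariate rules.

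The early-effect argument does not touch demographics, treatment history or family history, and the plan does not say that every candidate comes from the call. It applies to clinical measures from that call.

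Finally, the sample size and the 75% use criterion do not depend on covariates. That is fair, but Hypothesis 1b compares outcomes with TAU and section 17.0 plans effect models.

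**Conclusion.** The concern holds as one of precision, pre-specification and possible attenuation. The documents do not support a claim of inflated type I error, or of a large distortion from ignoring clinic in the tests.

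The precision loss, about 18% in SD, rests on an assumed covariate-outcome correlation of 0.6; a weaker predictor would gain less. The attenuation, from 0.50 to between 0.42 and 0.32, is conditional. It needs an early effect of 0.3 to 0.5 SD on a prognostic call variable, in the same direction as the later effect, and the documents give no estimate of one. The order of events makes it possible, and section 16.0 describes the intervention as immediate. The number of clinics, ICC, significance level and number of candidate variables are also assumptions. This is a moderate weakness in a pilot, and cheap to remove.

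**What to change.** In section 17.0:
- Delete the selection of covariates by baseline tests, and present baseline characteristics by condition descriptively, without p-values.
- Name a short prognostic list, measured before BRITEPath starts, for every effect model: age (date of birth is collected), the pre-intervention clinic PHQ-9 from the medical record, and sex if it is recorded among the sociodemographic items, since the documents do not name it.
- Include clinic as a random effect, and period, in every effect model.
- State that clinical variables from the post-intervention baseline call will not be used as adjustment covariates.

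**Cost.** Analysis wording only; no new visits or participants. The record PHQ-9 has no stated timing, so the text must require a score dated before BRITEPath starts. It will be missing where no PHQ was available at referral (section 10.0) or where the participant declines record access (section 14.0). A simple missing-value rule is therefore needed, fixed before the data are seen. A few degrees of freedom are used. In the assumed layout, fixed clinic effects would bring the model to about 5 + 5 + 1 + 3 = 14 parameters (clinics, period contrasts, treatment, covariates) for 50 participants, which is a reason to treat clinic as random and keep the list short.

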1.0 Study Summary

Study Title	BRITEPath-ETUDES Phase 1b
Study Design	Stepped wedge randomization; We will evaluate BRITEPath’s feasibility and efficacy compared to treatment as usual care (TAU) across sites.
Primary Objective	We will create and rapidly iterate user interfaces to develop the three components of BRITEPath: (1.) Guide2BRITE, an electronic guide for mental health clinicians providing step-by-step instructions in the onboarding of the safety plan, emotion regulation, and distress tolerance skills for (2.) the BRITE app, a personalized and interactive safety plan and self-monitoring tool for the adolescent; and (3.) the clinician dashboard, BRITEBoard, to track adolescents’ app use, distress, and treatment progress as well as to promote communication and collaboration among mental health and primary care providers.
Secondary Objective(s)	We will test BRITEPath's impact compared to TAU utilizing a stepped wedge design and a RE-AIM framework. BRITEPath focuses on novel approaches to support treatment and management of adolescent depression and suicidality in pediatric primary care and community mental health settings.
Research Intervention(s)/ Investigational Agent(s)	Mobile App based intervention
IND/IDE #	n/a
Study Population	12-26 yo patients seeking mental health treatment
Sample Size	50
Study Duration for individual participants	12 weeks
Study Specific Abbreviations/ Definitions	BRITEPath=BP Guide2BRITE=G2B BRITE=app used on participant Mental health=MH Behavioral health=BH

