We will develop an app-based intervention, BRITEPath that enhances the capacity of pediatric primary care to effectively manage depressed and suicidal adolescents by referral to embedded MH services. BRITEPath includes three components delivered by MH clinicians, including (1.) an electronic on-boarding procedure tool that supports MH clinicians, Guide2Brite; (2.) the adolescents' safety planning app, BRITE; and (3.) the clinician dashboard, BRITEBoard, to facilitate treatment planning and communication with other primary care providers.

2.2 The aims and hypotheses related to this specific protocol and submission are below for Phase 1b. Aims of the previous phase are in a University of Pittsburgh OSIRIS IRB protocol submission (#PRO18050281) entitled ETUDES Phase 1a-qualitative. Aims of later phases described briefly will be submitted in subsequent protocols.

PROTOCOL TITLE: The Center for Enhancing Treatment & Utilization for Depression and Emergent Suicidality Phase 1b-Study 3-BRITEPath

We will test the feasibility of using BRITEPath in community & pediatric practices using a stepped wedge design. We hypothesize that participants, parents, and clinicians will find the intervention usable and feasible to deploy. We will assess the impact of BRITEPath alone (compared to its impact as part of iCHART in later phases of the ETUDES Center, by obtaining follow-up phone assessments on suicidality, depression, and functional status at 4 and 12 weeks after intake.

Aim 1b (Phase 1b, Feasibility). We will pilot BRITEPath in sites using a stepped wedge design (50 adolescents aged 12-26 yo). Hypothesis 1b: The use of BRITEPath will decrease depressive symptoms, distress, and suicidality (any self-injurious ideation, urges, or behavior) as well as improve overall functioning compared to TAU.

Criterion for success: 75% of adolescents who receive BRITEPath will use it, and 75% of MH clinicians will use Guide2BRITE and BRITEBoard.

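### The only between-condition model with a named outcome is for readiness; no outcome or model form is specified for comparing BRITEPath with TAU on any Hypothesis 1b outcome

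*Combined protocol and SAP*

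**What the plan says.** The comparative claim appears in three places.

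- Section 1.0, secondary objective: "We will test BRITEPath's impact compared to TAU utilizing a stepped wedge design and a RE-AIM framework".
- Section 2.0, where the hypothesis for the pilot reads "The use of BRITEPath will decrease depressive symptoms, distress, and suicidality (any self-injurious ideation, urges, or behavior) as well as improve overall functioning", with TAU as the comparator. The same section places follow-up calls on suicidality, depression and functional status at 4 and 12 weeks after intake.
- Section 6.0 says that the pilot will give an effect size against TAU for suicide risk, to be used in designing a larger trial if results are promising.

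The analysis plan is in section 17.0. The paragraph that takes up the hypothesis contains four statements, in this order:

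1. "We will perform multilevel modeling to explore time- and intervention-level factors associated with BRITEPath’s use".
2. "We will first conduct t-tests for continuous variables and chi-square tests for categorical variables to examine baseline differences in demographic and clinical variables".
3. "We will use generalized linear mixed models (nesting for site) to examine between intervention differences in readiness".
4. "Distinguishing characteristics will be included as covariates in models examining treatment effects".

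Section 17.0 then lists the RE-AIM measures. Efficacy is the percentage of patients with clinically meaningful improvement in depression, suicidality and functioning.

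**The concern.** The paragraph that should say how Hypothesis 1b is tested attaches its one between-condition model to a variable outside that hypothesis. Readiness for treatment is one item in the list of call measures in section 6.0, and no aim or hypothesis mentions it.

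An analyst who follows the text literally reports a TAU contrast on readiness, and has no instruction for suicidality, depression or functioning. An analyst who fills the gap must choose the outcome, the time point and the model, possibly after seeing the data. Four domains at two follow-up times give 4 × 2 = 8 candidate contrasts, or 3 × 2 = 6 if distress is set aside. An effect size picked from these after the fact would be a poor basis for planning the larger trial.

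**Working it through.** This point rests on text, so the check sets what is hypothesised beside what is specified.

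**Each statement in the section 17.0 paragraph**

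1. Multilevel model: the outcome is use of BRITEPath. This serves the feasibility claim and the 75% use criterion in section 2.0. It is not a Hypothesis 1b outcome and states no TAU contrast.
2. t-tests and chi-square tests: baseline variables only.
3. Site-nested generalized linear mixed model: a between-condition contrast, with readiness as outcome.
4. Covariate rule: refers to treatment-effect models, but gives no outcome, link, contrast or time point.

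**Each Hypothesis 1b domain**

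| Domain | Where its measurement is described | Named outcome of a model against TAU | In RE-AIM Efficacy |
|---|---|---|---|
| Depressive symptoms | Follow-up calls, weeks 4 and 12 (2.0) | No | Yes, percentage only |
| Suicidality | Follow-up calls, weeks 4 and 12 (2.0) | No | Yes, percentage only |
| Functioning | Follow-up calls, weeks 4 and 12 (2.0) | No | Yes, percentage only |
| Distress | Ratings in the app (5.0, 15.0) | No | No |

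The count is 0 of 4 domains with a specified analysis against TAU, and 3 of 4 with a responder percentage that carries no TAU contrast.

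**Other places that might fill the gap.** Section 4.0 is titled as the endpoints section but contains only rules for discontinuing a participant. Section 6.0 lists call measures without linking them to analyses, and says that the full set of measures is available on request.

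**The plan's one precision figure.** Section 17.0 gives a 95% CI width of no more than 0.28 with 50 participants. The Wald width for one proportion is 2 × 1.96 × √(p(1 − p)/n). With p = 0.5 and n = 50 it is 2 × 1.96 × √(0.25/50) = 0.277, so the figure reproduces. At the 75% success criterion it is 2 × 1.96 × √(0.1875/50) = 0.240. Both are one-sample feasibility widths. They give no precision for a BRITEPath-versus-TAU difference, so the sample-size text does not identify the comparative outcome either.

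**The case against.** The strongest reply is that the analysis is under-specified rather than absent. The covariate sentence commits to treatment-effect models in the paragraph that addresses the hypothesis, and the only treatment effects hypothesised are those of Hypothesis 1b. This stands. A reader might infer that no Hypothesis 1b outcome will be compared with TAU at all. The documents do not support that. They show the intention and leave the content open.

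A second reply is that the readiness model may be a preparatory step: compare baseline characteristics, compare readiness, then adjust for whatever differs. This is plausible. On that reading readiness is not misplaced, but the treatment-effect models still have no stated outcome.

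A third reply is that section 1.0 ties RE-AIM to the comparison with TAU, and RE-AIM Efficacy names three of the four domains. Those outcomes are therefore in the plan. Even so, the Efficacy item gives no contrast, model or threshold for improvement.

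A reader might also infer that the model of use must break down, because TAU participants have no use to model and the condition effect could not be estimated. The plan never says that TAU participants enter that model. It also does not say that their use is always zero: steps are about 3 months and follow-up is 12 weeks, so a site could switch while a TAU participant is still being followed. No such failure can be charged to the plan.

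Finally, this is a pilot whose sample size and success criterion rest on feasibility. That stands, and it limits the severity.

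**Conclusion.** The point holds as a failure of specification. The only between-condition model with a named outcome concerns a variable outside every hypothesis, and 0 of the 4 Hypothesis 1b domains has a stated outcome and model form for comparison with TAU. This is more than missing detail, because the outcome that is named does not match the hypothesis the paragraph says it addresses.

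It should be fixed before analysis. It does not threaten the feasibility conclusions and does not call for more participants. What is at risk is the credibility of the TAU contrast and of any effect size carried into the later trial.

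Two assumptions apply. First, TAU participants are taken to receive the same week 4 and week 12 calls as BRITEPath participants; the stepped wedge comparison and the blinded follow-up assessors in section 6.0 imply this. Second, the measure set that is not reproduced in the protocol is taken to include usable scales for depression and functioning.

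**What to change.** Revise the analysis paragraph in section 17.0 as follows.

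- Make depressive symptoms, suicidality and functioning at weeks 4 and 12 the dependent variables of the mixed models, with condition (BRITEPath or TAU) as the tested term.
- Include a calendar-period term. In a stepped wedge the share of sites using BRITEPath rises over time, so without this term the condition effect is confounded with time.
- Include random effects for site and for participant, the latter because each participant contributes repeated measures.
- Name the instrument for each outcome and match the link function to it. The call list in section 6.0 names a suicide scale, but no depression severity scale.
- Keep readiness as an exploratory outcome or a baseline covariate, and say which.
- State that distress is described only as an app measure. Then either name a measure taken in both conditions or remove distress from the TAU comparison, so that hypothesis and analysis agree.
- State that the model of BRITEPath use is restricted to BRITEPath participants.

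The cost is a change of text in section 17.0, with a matching edit to Hypothesis 1b if distress is removed. For the three domains covered by the planned calls, no new participants or visits are needed. A distress measure in both conditions would add an item to the calls if none is already in the full measure set.
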